Patients with frequent or and intense eating disorder pathology, or medical symptoms related to their eating disorder must receive clearance from their primary care physician (PCP) before they can be considered eligible for participation in this study. PCPs will be asked to provide measurements of height, weight, vital signs, and blood draws. PCPs will be notified via letter of their role in determining eligibility for the study and will be provided contact information for the study PI if they have any questions or concerns. Individuals who are or become medically unstable for outpatient treatment will be referred for appropriate medical treatment. Patients must also agree to allow study staff to communicate with their PCP throughout the study and to be reassessed for medical stability if there is a worsening in symptoms. Once a participant is enrolled in the study, study therapists/staff and the PCP will jointly determine the appropriate level of medical care outside of study visits to ensure the participant remains medically stable for outpatient treatment. If patients become medically unstable for outpatient treatment or show a significant and continued worsening in symptoms, they will be removed from the study and referred to a higher level of care. The procedures for medical management of the study patients described above have been successfully utilized by our lab in prior studies of patients with binge eating spectrum disorders. After potential participants are deemed eligible a baseline assessment will be completed. If participants are found to be ineligible at any stage of the process, participants will be given referrals if desired.

Following the baseline assessment, participants will be randomized to receive one of the four treatment conditions and will receive 12 weeks of treatment.

Plans for assessing and/or intervening on suicidal ideation or risk for serious self-harm.

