Eating disorders can be medically dangerous, particularly if the individual is of low weight or engaging in frequent or severe compensatory behaviors. Thus, careful monitoring of treatment progress is essential. It is possible that some research participants may develop Anorexia Nervosa or display dangerous electrolyte imbalances due to purging. In this case, the research participant will be removed from the study and referred to a more appropriate level of care (e.g., intensive outpatient, inpatient treatment). The process for tracking this information and making referrals to a higher level of care is described below.

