Some research participants undergoing treatment may become uncomfortable or anxious. Research participants will be asked to abstain from binge eating and purging, a process that is difficult given the nature of the illness. Research participants will also be asked to provide information regarding a number of significant health behaviors during the assessments. However, all assessment instruments have been used in past research without incidence and research participants will be informed that they can skip questions or discontinue participation at any time. Although we expect most research participants to show a reduction in disordered eating symptoms, it is possible that some research participants could experience a worsening of eating disorder symptoms during the study period. If a worsening of symptoms is identified, we will follow the protocol described below to ensure the safety of research participants. This protocol is based on those used in our team's current NIH funded trials for BN and BED. If a coach identifies worsening binge eating symptoms or compensatory behaviors, the principal investigator and research coordinator will be notified. If the increases in disordered eating symptoms are determined to be transient, mild, and unlikely to result in adverse health consequences, efforts will be made to keep the research participant enrolled in the current study and treatment condition consistent suggestions will be made to address current symptoms. If the increases in eating disorder symptoms are sustained, clinically significant, or likely to cause health consequences, we will consult with the research participant's PCP to discuss whether medical management is needed. Research participants with frequent and intense eating disorder pathology will be medically monitored by their PCP throughout the trial and will only be allowed to participate if it is deemed medically appropriate by their PCP. Research participants will be informed that research personnel will inform the PCP if there is a change in symptom status such as an increase in restrictive eating behavior or increase in purging behavior that may require additional medical management. It is expected that these research participants will have regular appointments with their PCP, the frequency of which will be determined by the treating physician. In order to facilitate care, consent will be obtained prior to treatment onset for two-way communication between study staff and the treating physician. As part of the trial, treating physicians will also be provided current practice guidelines as set forth by the American Academy of Psychiatry regarding eating disorders. Research participants without a PCP, with limited access to their PCP, or with a PCP that is unable to effectively monitor their eating disorder symptoms, will be assisted in locating a PCP that better fits their needs. We will not be

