
PROTOCOL TITLE: Using factorial design to examine efficacies of technology-based augmentations for improving treatment adherence and skills utilization in a self-help CBT program for binge eating.

Protocol Version Date: April 19, 2022

covering any costs for PCP visits or related fees. Ongoing participation in the trial will be contingent upon continued medical management. If, at any time, the treating physician determines that the health of the research participant precludes continuation of outpatient treatment, a meeting will be scheduled with the treating physician, research participant, and study staff to assist in locating referrals for appropriate levels of care. If a higher level of care is sought, research participants will be removed from the trial.

16) Potential Benefits to Subjects

All efforts will be made to minimize the risk to research participants in this study, with medical monitoring occurring on a regular basis and research participant data being securely stored. The proposed treatment includes elements that have been shown to lead to decreased symptomatology in research participants with clinically significant binge eating and comorbid syndromes, and to improve quality of life and associated distress. Thus, it is expected that research participants will directly benefit from the study intervention. Also, the standard of care for binge spectrum eating disorder and bulimia nervosa is behavioral treatment. In this project, all the participants will receive self-help CBT program based on [name] evidence-based treatment program for binge spectrum eating disorders, which is superior to standard of care. Indirect benefits include increased knowledge regarding treatment for clinically significant binge eating, which will improve interventions for future research participants and could decrease the impact of this illness on society by way of decreased health care costs and disability. As such, the benefits of this study far outweigh the potential risks.

17) Vulnerable Populations

Does not apply

18) Multi-Site Research

Does not apply

19) Community-Based Participatory Research

Does not apply

20) Sharing the Results with Subjects

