Participants will have access to their own personal survey and interview results upon request; however, researchers will not share data with each participant as part of study protocol. If participants request their data, they will be provided with a password protected excel file with their own response. A password will be sent in a separate email to ensure protection of data. If the research participant doesn't have access to a computer, they can be provided a paper copy of their responses.

Additionally, information will be shared with the subject's primary care physicians. Medical status will be closely monitored throughout the intervention by the PCP and patients will be required to have additional medical evaluations if they show a deterioration in symptoms. Participants will be required to sign consent to contact their PCP throughout the study to ensure coordination in care. The PCP will be provided with a letter describing enrollment in the study

PROTOCOL TITLE: Using factorial design to examine efficacies of technology-based augmentations for improving treatment adherence and skills utilization in a self-help CBT program for binge eating.

Protocol Version Date: April 19, 2022

and provide detailed information on the medical management of transdiagnostic binge eating. Participants will be informed that their coach/study staff will inform the PCP if there is a change in symptom status such as an increase in restrictive eating behavior or an increase in purging behavior.

21) Setting

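### With DDS OFF, no one is assigned to check app entries for worsening symptoms, and withdrawn participants' data are to be discarded

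*Protocol*

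**What the plan says.** Protocol section 15 (Risk to Subjects) treats careful monitoring as essential, because anorexia nervosa or dangerous electrolyte imbalance could develop. It adds: "The process for tracking this information and making referrals to a higher level of care is described below". The text that follows opens without reference to condition, "If a worsening of symptoms is identified, we will follow the protocol described below to ensure the safety of research participants", and then gives the operative step: "If a coach identifies worsening binge eating symptoms or compensatory behaviors, the principal investigator and research coordinator will be notified".

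Section 10 restricts coaches to the DDS-ON conditions. There they use the portal to write weekly emails and meet weekly with their supervisor to go through adherence, skills and self-monitored data. With DDS OFF, data are not shared and no coach emails are sent. Participants in all four conditions record eating behavior in the app several times a day (section 10, Skill utilization).

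Some safety provisions do not depend on condition. Under Screening in section 10, study staff and "the PCP will jointly determine the appropriate level of medical care outside of study visits". Section 20 says "Medical status will be closely monitored throughout the intervention by the PCP" and "Participants will be informed that their coach/study staff will inform the PCP if there is a change in symptom status". Section 15 expects regular PCP appointments for people with frequent and intense pathology, "the frequency of which will be determined by the treating physician". The study will not be "covering any costs for PCP visits or related fees", but staying in the trial depends on continued medical management.

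Section 14 (Withdrawal of Subjects) lists hospitalization, suicidal ideation and failure to comply among the grounds for withdrawal. It says the data of those terminated are to be destroyed or barred from use.

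**The concern.** The role that section 15 relies on to notice worsening is part of a randomised factor. Two of the four conditions lack it, and the section names no substitute. Participants in those conditions face the same clinical risk and enter the same kind of data, but nobody has the task of reading those entries for safety.

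The main stake is safety. The second is the analysis. Sustained worsening can lead to removal (section 10, Screening), and section 14 withdraws people for events related to outcome. Discarding their records takes out data that bear directly on the efficacy aims. This second problem exists whether or not detection differs by DDS.

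**Working it through.** The documents give no figure to reproduce, so the check sets every route by which worsening could be noticed during the 12 treatment weeks side by side.

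| Route | Protocol section | Conditions | Schedule | Looks at app entries for worsening? |
|---|---|---|---|---|
| Coach and supervisor review | 10 (Advanced DDS; high-quality interventions) | DDS ON only | Weekly | Sees self-monitored data; purpose is treatment support; no safety threshold |
| Study assessments | 10 (Assessment Procedure; Feedback Questionnaire for timing) | All | About weeks 6 and 12 | No; interview and questionnaires |
| Staff act once aware | 10 (suicidal ideation), 13 | All | None | No one assigned to look |
| Staff report changes to PCP | 15, 20 | All | None | How staff learn of a change is not stated |
| PCP monitoring | 15, 20 | All; regular appointments for frequent and intense pathology | Set by the physician | No PCP access to app data described |
| JITAI algorithm | 10 (JITAI) | JITAI ON | Automated | Messages the participant; no alert to staff described |
| Staff download of app data | 12 | All | Regular, no interval given | A data-security step |
| Staff review of assessment data | 11 | All | Not given | For accuracy and completion |

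Only the first row is both scheduled between assessments and directed at self-monitored data, and it is absent with DDS OFF.

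**Scale.** Two of four conditions have DDS OFF. If allocation is equal (an assumption), 76 × 2/4 = 38 participants, or 76/4 = 19 with JITAI only and 19 with neither factor. Scheduled study-side looks during treatment are weekly with DDS ON, against weeks 6 and 12 with DDS OFF, so 6 weeks apart. These are intervals between scheduled looks. They do not measure delay in detection, because the chance that a coach would notice worsening and the timing of PCP visits are both unknown.

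**Data loss.** The SAP (Statistical Design and Power) relies on likelihood-based estimation and multiple imputation, with sensitivity analyses if missingness depends on the missing outcome.

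1. Both main methods draw on what was observed before a participant left. Someone withdrawn after mid-treatment would normally contribute baseline and mid-treatment values.
2. If section 14 is followed as written, that person contributes nothing, and the analysis covers only those not withdrawn.
3. Hospitalization and suicidal ideation are plausibly related to outcome, so the people lost are unlikely to be a random subset.
4. Section 24 encourages people who stop treatment to keep attending assessments, so retention fits the plan's own aim.

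The SAP's power section allows for up to 15% attrition. It does not say how much of this would be withdrawal by the study, so the number of records lost cannot be derived.

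**The case against.** The strongest reply is that the coach sentence is one example and not the whole system. It follows a trigger that applies to everyone. Section 13, the designated safety section, speaks of the study team and study staff, and section 20 pairs coach with study staff. The coach sentence is also as conditional as the staff clauses. The highest-risk participants, those purging three or more times a week, need PCP clearance to enter, and continued participation depends on medical management in every condition. All of this stands. A reader might infer that DDS-OFF participants have no safety net, and the documents do not support that.

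The reply also holds that the DDS-ON advantage is itself inferred. The portal is described as gathering module uptake, self-monitoring compliance and skills data for a supportive email. The content of the monitoring forms is in a separate document. The data listed under section 12 include binge eating but do not mention purging or weight. This stands too, and it rules out saying that worsening will be found sooner with a coach.

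A last objection is that safety contacts with DDS OFF add human contact to conditions defined by its absence. That is a real cost, but a limited one if contact is confined to safety.

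What the reply does not supply is any role, in any section, charged with checking app entries for worsening when DDS is OFF.

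**Conclusion.** The concern holds in limited form. Section 15 promises a tracking process, but the only in-study role it names as identifying worsening is absent from two of four conditions, about 38 of 76 participants under equal allocation. Detection there may be later or less frequent. A reader might go on to put a number of weeks on the delay, or to claim a biased DDS effect. Neither follows: any such figure needs assumed detection rates and PCP intervals, and plausible choices include no difference at all.

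The discarding of withdrawn participants' data is a separate defect that does not depend on coaches. It rests only on section 14 being applied as written. Its direction and size cannot be derived from the documents.

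**What to change.** **1. One safety flag for all conditions.** Run an automated symptom flag on the app data already collected, with the same threshold and a fixed schedule (for example weekly) in all four conditions. Send it to the investigator and not to coaches, and limit any contact to safety, with no adherence or skills advice. Change the section 15 trigger to a coach or any study staff member. State in section 10 that DDS OFF means data are not shared with coaches. The sponsor should set the clinical threshold and confirm that the forms capture compensatory behaviors.

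**2. Keep the data.** Amend section 14 so that data already collected from withdrawn participants are retained and analysed, as consent allows. Log flags, actions and removals by condition.

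**Cost.** Wording changes, one query over 76 × 12 = 912 participant-weeks, and a log. The number of DDS-OFF contacts depends on the threshold. As an assumption, if 5–10% of participants were ever flagged, that is 38 × 0.05 to 38 × 0.10, about 2 to 4 people. If 5–10% were flagged each week, 38 × 12 = 456 participant-weeks would give about 23 to 46 flags. A specific threshold keeps the dilution of the DDS contrast slight. Some asymmetry would remain if DDS itself increases logging.

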## STATISTICAL DESIGN AND POWER

Descriptive statistics and exploratory graphing for all variables at all time points will be examined. We will compare baseline characteristics between treatment conditions using ANOVA for continuous variables and a chi-square test for categorical variables. Baseline variables that differ by treatment condition will be considered for use as covariates in the analyses described below. Patterns of missing data will be examined. Likelihood-based estimation methods and multiple imputation models will be used to handle missing data. If the missingness mechanism is related to the missing outcome itself, we will use sensitivity analyses to explore how robust our findings are with respect to a range of assumptions regarding missing data.

Primary Aim 1. To test target engagement of each intervention factor, we will model the pattern of change in treatment adherence and skills utilization separately over time using multilevel models (PROC MIXED in SAS). The first level will model individual participant's treatment adherence (or skills utilization) over time with baseline as time 0. At the second level, the individual intercept and slope will be entered as outcomes with each intervention factor as a predictor. We will examine each of the two intervention factors separately. The cross-level interaction between time and the intervention factor will be used to determine the effect of the intervention component on the pattern of change in the treatment targets.

Primary Aim 2. To assess feasibility and acceptability (primary aim 2), we will assess feasibility estimate (a) recruitment success (n=76) and (b) retention (>75% through all assessments), and (c) satisfaction via Likert ( $\geq$ "high") and coded interview ratings utilized in our team's previous clinical trials and other studies.

Primary Aim 3. To examine the independent efficacy of the two intervention factors, we will model the pattern of change in binge eating frequency over time using mixed-effect models. This approach will allow us to account for the nested structure of the data, with assessment nested within participants nested within conditions. Covariance structure for the repeated measures will be determined based on the Akaike Information Criteria (AIC) and Bayesian Information Criteria (BIC). The cross-level interaction between time and the intervention factor (e.g., JITAs ON vs. OFF) will be used to determine the effect of the intervention factor on the pattern of change in binge eating frequency. Both intervention factors will be examined separately. Similarly, we will model the pattern of change in EDE global scores over time using generalized mixed-effect models. The cross-level interaction between time and the intervention component will be used to examine the effect of the intervention factor on change in EDE global scores. In addition, statistical contrasts will be performed for both intervention factors on primary outcomes at post-treatment and 3-month follow-up.

Primary Aim 4. To test target validation of each intervention factor, we will test whether temporally precedent change in treatment adherence and skills utilization mediates the effect of each of the two intervention factors on primary outcomes. In particular, we will use the mediation model outlined by Preacher and Hayes to examine whether increases in treatment adherence and skills utilization by each factor from baseline to mid-treatment are associated with improvements in post-treatment outcomes and increases at post-treatment are associated with improvements in outcomes at 3-month follow-up. The bias-corrected bootstrap test will be applied to test the joint significance of the indirect pathways, which expands on Baron and Kenny's methods by providing additional guidelines and techniques that allow for the most robust and accurate interpretation of these mediating effects.

Exploratory Aim. To explore the component interaction effects, higher-order interaction terms (e.g., three-way interaction between Advanced Digital Data Sharing, JITAs and time) will be added to the mixed-effect models and the generalized mixed-effect models outlined in primary aim 1. Due to the model complexity and limited statistical power for this aim, effect sizes will be relied upon for interpretation.

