Addition of intervention factors to self-help CBT program to accomplish factorial design. As mentioned above, participants will be randomized to one of the 4 treatment combinations. The standard of care for binge spectrum eating disorder and bulimia nervosa is behavioral treatment. In this project, all the participants will receive self-help CBT program based on [name] evidence-based treatment program for binge spectrum eating disorders, and is superior to standard of care. As such, there is no potential of randomizing subjects into a condition that is less than standard of care for their eating disorders. Below, we describe the treatment when each of the two intervention factors are turned ON and OFF and when synergies occur between both intervention factors, as applicable.

Advanced Digital Data Sharing with Coaches When Advanced DDS with Coaches is turned ON, coaches having a bachelor's degree in health-related fields (e.g., psychology, nursing, nutrition etc.) will have access to a secure web portal called the digital data portal. Our team has successfully developed and used a digital data portal for ED treatments in a recent CBT+ clinical trial (R34MH11602). This portal will accomplish four key functions including, 1) gather data on target behaviors from the base self-help app (i.e., uptake of weekly module, self-monitoring compliance and skills utilization), 2) synthesize participants' behavioral data on treatment targets, 3) flag data to increase salience of behaviors needing improvement and 4) use sophisticated algorithms to generate recommendations for intervening on the identified data patterns. Using the information from the digital data portal, the coaches will send weekly emails to facilitate improvement in treatment targets. Coaches will send one email a week for a total of 12 emails over the course of treatment.

When Advanced DDS with Coaches is turned OFF, participants' will not have their data shared and will not receive emails from the coaches.

Just-in-time, adaptive interventions (JITAI) The proposed JITAI system will use machine learning algorithms to intervene on 1) treatment adherence, and 2) skills utilization during the 12 weeks of treatment. When JITAI are turned ON, the base self-help app will be used to deliver targeted, personalized and automated interventions during machine learning

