PROTOCOL TITLE: Using factorial design to examine efficacies of technology-based augmentations for improving treatment adherence and skills utilization in a self-help CBT program for binge eating.

Protocol Version Date: April 19, 2022

algorithm-identified moments when participant could benefit from receiving an intervention for improving two key areas including 1) treatment adherence, and 2) skills utilization based on responses (or lack thereof) in self-help app. For example, JITAIs will be delivered during times when treatment adherence is low (e.g., when participant has missed tracking for several days in a row, when participant has not updated weekly goals on the self-help app). JITAIs may deliver an intervention educating about relationship between low adherence and poor outcomes and suggest strategies to make progress in the following days. JITAIs will also be delivered during times of machine learning algorithm-identified moments when treatment skills use may be beneficial (e.g., participant reports an urge to binge, report skipping a meal/snack). In this case JITAIs may deliver interventions encouraging use of specific skills with brief instruction for skills implementation. For example, if a patient reports having an urge to engage in binge eating, the machine learning algorithm will identify that this patient is at risk for a binge episode in the near future. As a consequence, the JITAIs system will send automated interventions to coach a person on using urge management skills to prevent binge eating occurrence.

When JITAIs are turned OFF, participants will not receive interventions in real-time on the base self-help app.

When Advanced DDS with Coaches and JITAIs are both ON, while participants will continue to receive machine learning informed interventions, coaches will also have the ability to create and send interventions via the digital data portal to provide additional support. For instance, coaches will have the ability to write an intervention and schedule its delivery at a time when they believe participant will be at high risk for ED symptoms.

Consent procedures.

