Assessments will be conducted by unblinded assessors at baseline, mid-treatment, post-treatment, and at 3-month follow-ups. Assessments will be for a total of 3 hours in length. Assessors for the baseline, mid-treatment, post-treatment, and 3 month follow up will be research coordinators employed and paid by the WELL Center and Ph.D students at Drexel University. Three hours of the assessment is a semi-structured interview in which the participants will be using a zoom link via Drexel's HIPAA compliant Zoom platform the assessor sent prior to the interview to meet with the assessor who conducts the interview with the participant. Total length of participation in this study will be about 7 months from the baseline assessment to the 3-month follow-up assessment. As the study continues, the status of the trial will be updated on <http://www.ClinicalTrials.gov> as different phases of the study start and end (including but not limited to “not yet recruiting”, “recruiting”, “active not recruiting”, and “completed”).

This study will have 2 kinds of blind assessors. One type of blind assessor is the study coordinator. The study coordinator is a full-time paid employee on the study. As part of their job responsibilities, they will conduct assessments for this current study. The other type of assessors is graduate students. Students serve as assessors on clinical trials being conducted in a research lab to receive specialized training and supervision in conducting clinical interviews for assessing eating disorders. Typically, graduate students are obligated to fulfill 8 hours of training time in the specialized research lab without getting paid. Graduate students will be asked to conduct assessments within these 8 hours of free lab time and hence, will not be paid for conducting the assessments. In the conditions with Advanced DDS with Coaches, coaches will be unblinded throughout the 12-week program. Coaches will know the study condition and diagnosis of the specific patients they've been assigned in order to facilitate improvement in treatment targets of the patients they've been assigned. Coaches will be blinded to the clinical outcomes from treatment for the patients they are assigned to. They will be blinded to all clinical outcomes data collected at different assessment time points.

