### Power Analysis

The study's data will consist of repeated assessments over time within randomized individuals within conditions. Therefore, power calculations are dependent on both an expected effect size of the intervention factors as well as the clustering of the data, resulting in a mixed-effect model structure. We conducted power analysis using the method described by Raudenbush and implemented with the software Optimal Design. For target engagement, effect sizes are estimated from a meta-analysis evaluating 11 clinical trials of self-help CBTs augmented with technology-based intervention factors for transdiagnostic binge eating showed large effect size improvements in treatment adherence (defined as accessing treatment resources and adherence to treatment prescription) ( $d = 0.78$ ). A sample size of 76 would be necessary for 80% power to detect a large effect of condition with alpha of 0.05 and three assessment points, assuming the ratio of the variability of level-1 coefficient to the variability of level-1 residual is one. For independent efficacy of intervention factors

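### The DDS analyses and power figures have no coach term, although only DDS-ON participants have coaches; if coaches differ, the DDS intervals are too narrow for conclusions beyond these coaches

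*SAP*

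**What the plan says.** Coach contact belongs to one level of one factor. In Protocol section 10, under Advanced Digital Data Sharing with Coaches, the ON level provides weekly contact: "Coaches will send one email a week for a total of 12 emails over the course of treatment". OFF participants "will not have their data shared and will not receive emails from the coaches". Caseloads are individual; under Assessment Procedure the protocol states: "Coaches will know the study condition and diagnosis of the specific patients they've been assigned". When both factors are ON, "coaches will also have the ability to create and send interventions via the digital data portal to provide additional support".

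The models stop at the participant. For Aim 1 the SAP has two levels, time and person: "At the second level, the individual intercept and slope will be entered as outcomes with each intervention factor as a predictor". For Aim 3 the structure is "with assessment nested within participants nested within conditions". The Power Analysis section describes the data as "repeated assessments over time within randomized individuals within conditions". The SAP text available for review contains no coach term, number of coaches or coach ICC, and neither document gives a rule for assigning participants to coaches. The opening part of the SAP was not available.

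**The concern.** One coach serves several participants in DDS-ON and none in DDS-OFF, so the design is partially nested. If some coaches are more effective than others, outcomes of participants who share a coach are correlated. A model without that correlation treats 38 DDS-ON participants as 38 independent pieces of information about what coached DDS does. The DDS-by-time standard error in Aims 1 and 3 is then too small and the test rejects too often.

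This matters in a pilot because the SAP says it will rely on effect sizes and their confidence intervals for EDE global and use them to design a larger trial. That trial would also need an idea of the coach ICC, which cannot be recovered unless it is recorded who coached whom.

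**Working it through.** **1. The plan's own figure.** Inputs from the SAP Power Analysis: d = 0.78, four assessments, alpha 0.05 (two-sided assumed), and a ratio of slope variance to residual variance of 1. In the Raudenbush linear-change method, with residual variance set to 1:

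- V = 12 / [(M−1)M(M+1)] = 12 / (3 × 4 × 5) = 0.2
- noncentrality = N d² / [4(1 + V)] = 64 × 0.6084 / 4.8 = 8.112
- power from the noncentral F with 62 df = 80.1%

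This reproduces the stated N of 64, and 64 / 0.85 = 75.3, rounded up to 76, reproduces the enrolment figure. The formula contains no coach variance, so the binge-frequency sample size has no allowance for it. The same formula gives 79 for EDE global (stated 78). For adherence with three assessments it gives 80 at d = 0.78, or 76 if the large effect is read as d = 0.80 (stated 76).

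**2. Effect of an omitted coach term.** Assumptions: 38 participants per DDS level (76 / 2; the ratio is not stated), k coaches with equal caseloads m = 38/k, and an ICC for the participant-level slope.

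- design effect in DDS-ON: DE = 1 + (m − 1) × ICC; in DDS-OFF it is 1
- variance ratio for ON minus OFF: R = (DE + 1) / 2
- actual error rate = 2 × [1 − Φ(1.96 / √R)]

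Example with k = 2 and ICC 0.05: m = 19, DE = 1 + 18 × 0.05 = 1.90, R = 1.45, √R = 1.204. The error rate is 2 × [1 − Φ(1.628)] = 10.4%.

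| Coaches | ICC 0 | 0.01 | 0.02 | 0.05 | 0.10 |
|---|---|---|---|---|---|
| 2 | 5.0% | 6.0% | 7.1% | 10.4% | 15.5% |
| 3 | 5.0% | 5.7% | 6.4% | 8.5% | 11.9% |
| 4 | 5.0% | 5.5% | 6.0% | 7.5% | 10.1% |
| 6 | 5.0% | 5.3% | 5.6% | 6.6% | 8.2% |

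A simulation of the coach-blind test (40,000 runs per cell) agrees within about 0.3 points. Over 2 to 6 coaches, the ratio of true to reported standard error is 1.01–1.09 at ICC 0.01–0.02, 1.07–1.20 at 0.05 and 1.13–1.38 at 0.10.

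**3. What adjustment costs.** Treat coaches as sampled, with approximate Satterthwaite df = (DE + 1)² / [DE²/(k − 1) + 1/37] and noncentrality √[76 × 0.6084 / (4.8 R)]. At N = 76 and ICC 0.05, power for d = 0.78 is about 35%, 60%, 70% and 78% with 2, 3, 4 and 6 coaches. Without clustering it is 86.5%. With 2 coaches it is only about 64% even at ICC 0, because about 4 df remain. With one coach, coach and DDS cannot be separated by any model.

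**The case against.** The strongest reply is that the inflation is conditional. At ICC 0 the test is exact, and at ICC 0.01 with 4 to 6 coaches it is 5.3–5.5%. Contact is one email a week built on portal-generated recommendations, and coaches review cases together weekly (Protocol section 10). The discretion to write their own interventions applies only when both factors are ON. Nothing in the documents points to an ICC as high as 0.10. If the conclusion is limited to the coaches actually used, the planned test is not inflated: simulation with fixed, centred coach effects gave 4.4–5.0%. All of this stands. It limits the size of the problem but does not supply a missing coach ID, number of coaches or scope of inference.

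Three stronger readings are tempting, and the documents do not support them.

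- *Condition is fitted as a random level, leaving almost no degrees of freedom.* The nesting phrase is loose. However, Aim 1 enters each factor as a predictor, Aim 3 tests the time-by-factor interaction and the exploratory aim adds a three-way product term. These are fixed effects, and the sample size reproduces with N − 2 df.
- *The plan ignores clustering altogether.* Repeated assessments within participants are a real cluster and are modelled. Coach is the evident unmodelled cluster on the treatment side.
- *Coach differences bias the JITAI comparison.* No allocation rule is stated, so imbalance cannot be asserted. In simulation the JITAI error rate stayed near 5% (4.5–6.2%) when coaches were allocated without regard to JITAI. It rose, to about 7–17%, only when they were allocated by JITAI status.

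**Conclusion.** The point holds in conditional form. The DDS analyses in Aims 1 and 3 and the power figures omit a possible coach effect that can exist only in DDS-ON. If coaches differ and the result is meant to reach beyond them, DDS intervals are too narrow. The excess over 5% is negligible to about 1 point at ICC 0.01, about 2 to 5 points at 0.05 and about 3 to 10 points at 0.10. This rests on equal allocation, equal caseloads, 2 to 6 coaches and a two-sided test; the number of coaches and the ICC are assumptions. The documents do not show that the error rate is in fact exceeded. The gap is worth closing because the pilot's intervals are meant to inform a later trial.

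**What to change.** - Record coach ID for every DDS-ON participant, and state the number of coaches.
- Assign DDS-ON participants to coaches from the randomization list, balanced over JITAI ON and OFF.
- Beside the planned DDS estimate, report a partially nested analysis (coach effect in DDS-ON only, small-sample df) or the DDS interval over a stated range of ICCs.
- With fewer than about four coaches, state instead that the DDS conclusion applies to these coaches only. A random coach term is too poorly estimated there to be a remedy.
- State in the Power Analysis that the figures assume no coach clustering.
- In Primary Aim 3 and the Power Analysis, say that condition (the two factors) is a fixed effect and not a level of nesting.

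The cost is SAP wording, one recorded variable and an assignment rule; sample size and treatment do not change. The real downside is that the coach-adjusted DDS interval is wider, markedly so with few coaches, which is why it belongs beside the planned estimate and does not replace it.
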